PT	Preferred Term
Q1; Q2; Q3	First Quartile; Second Quartile (median); Third Quartile
RCDC	Reverse Cumulative Distribution Curve
RNA	Ribonucleic Acid
SAE	Serious Adverse Event
SafAS	Safety Analysis Set
SAP	Statistical Analysis Plan
SD	Standard Deviation
SOC	System Organ Class (primary)
ULOQ	Upper Limit of Quantification
V	Visit
WHO	World Health Organization

1 Introduction

GRC90 is a study using the 2018–2019 formulations of quadrivalent inactivated influenza vaccine (Fluzone® Quadrivalent, Influenza Vaccine), recombinant influenza vaccine (Flublok® Quadrivalent, Influenza Vaccine), and high-dose trivalent inactivated influenza vaccine (Fluzone® High-Dose, Influenza Vaccine).

Influenza viruses types A and B belong to the genus *Orthomyxoviridae* and are characterized as enveloped, negative-strand, segmented ribonucleic acid (RNA) viruses. The viral envelope contains 2 virus-coded glycoprotein spikes, the hemagglutinin (HA) and neuraminidase (NA) proteins, which are key antigens in the host response to influenza virus in both natural infection and vaccination. A third protein, M2, is a minor envelope component of the A-strain viruses (1).

Vaccination with influenza vaccine is the primary method for preventing influenza and its severe complications. It has been shown to be effective in reducing influenza-associated morbidity and mortality in groups at increased risk for influenza-related complications such as infants and young children and persons 50 years of age and older. Of note, immune responses to the vaccine are lower in seniors than those in young healthy adults (2). Strategies to improve immune responses to the vaccine in the elderly population could provide significant additional reductions in influenza-associated morbidity and mortality. One approach is to increase the dose of HA in inactivated vaccines. Previous studies evaluating the immune responses in terms of hemagglutination inhibition (HAI) antibodies with higher doses of HA per strain in different influenza vaccines support a dose-response effect (3).

Fluzone Quadrivalent vaccine contains 4 influenza strains (A/H1N1, A/H3N2, and 2 B strains [1 each from the Yamagata and Victoria lineages]). In pre-licensure studies, Fluzone Quadrivalent vaccine induced antibody responses that were comparable to those induced by trivalent Fluzone vaccine with respect to the strains contained in each vaccine. Pre-licensure studies also demonstrated that the safety profile of Fluzone Quadrivalent vaccine was similar to that of trivalent Fluzone vaccine. Accordingly, Fluzone Quadrivalent vaccine offers the possibility of protecting against both B lineages simultaneously, without compromising vaccine safety (4) (5).

Flublok Quadrivalent vaccine is a recombinant HA influenza vaccine indicated for active immunization against disease caused by influenza A subtype viruses and type B viruses contained in the vaccine for adults 18 years of age and older. Flublok Quadrivalent vaccine contains 45 µg HA per virus strain per dose, 3 times the amount of HA compared to standard-dose quadrivalent inactivated influenza vaccine (SD-IIV4). This higher dose of antigen may be a particular advantage to older adults whose immune response to influenza vaccines can be suboptimal. In fact, in an efficacy study of approximately 9000 adults 50 years of age and older, Flublok Quadrivalent vaccine, compared to a SD-IIV4 comparator, demonstrated 30% to 43% greater efficacy in preventing laboratory-confirmed, protocol-defined influenza-like-illness caused by any viral type or subtype (6).

Fluzone High-Dose vaccine contains 60 µg HA per virus strain per dose, which is 4 times the amount of HA per strain per dose in Fluzone vaccine. It was developed for use in the elderly to

elicit enhanced immune responses against influenza through the use of higher antigen content. A large-scale efficacy trial, which was conducted during 2 influenza seasons (2011–2012 and 2012–2013) and involved more than 30,000 persons, showed that Fluzone High-Dose vaccine was 24.2% more effective than Fluzone vaccine in preventing laboratory-confirmed symptomatic influenza in persons 65 years of age and older. The results of the study met the FDA-agreed criteria for demonstrating superiority of Fluzone High-Dose vaccine compared with Fluzone vaccine for prevention of influenza disease in older adults (7).

During this study, Fluzone Quadrivalent, Flublok Quadrivalent, or Fluzone-High-Dose vaccine will be administered according to the guidelines in the Prescribing Information and only to persons for whom it is indicated.

The objectives of this study are to describe the safety and immunogenicity of Fluzone Quadrivalent vaccine in children 6 months to < 9 years of age and adults 18 to < 65 years of age, Flublok Quadrivalent vaccine in adults 18 to < 65 years of age, and Fluzone High-Dose vaccine in adults ≥ 65 years of age. An additional objective of the study is to provide available sera collected from subjects to the Center for Biologics Evaluation and Research (CBER) for further analysis by the World Health Organization (WHO), the Centers for Disease Control and Prevention (CDC), and the Food and Drug Administration (FDA) to support formulation recommendations for subsequent influenza vaccines. In addition, available sera from adult subjects may be further analyzed by the Sponsor to assess breadth of immune response induced by the study vaccines.

2 Trial Objectives

Safety

To describe the safety of the 2018–2019 formulation of Fluzone Quadrivalent vaccine in children 6 to < 36 months of age and 3 to < 9 years of age, and in adults 18 to < 65 years of age; the safety of the 2018–2019 formulation of Flublok Quadrivalent vaccine in adults 18 to < 65 years of age; and the safety of the 2018–2019 formulation of Fluzone High-Dose vaccine in adults ≥ 65 years of age.

Immunogenicity

To describe the immunogenicity of the 2018–2019 formulation of Fluzone Quadrivalent vaccine in children 6 to < 36 months of age and 3 to < 9 years of age, and in adults 18 to < 65 years of age; the immunogenicity of the 2018–2019 formulation of Flublok Quadrivalent vaccine in adults 18 to < 65 years of age; and the immunogenicity of the 2018–2019 formulation of Fluzone High-Dose vaccine in adults ≥ 65 years of age.

Serum Collection

To provide available sera (collected from subjects before vaccination [Blood Sample 1] and after final vaccination [Blood Sample 2]) to CBER for further analysis by the WHO, the CDC, and the FDA to support formulation recommendations for subsequent influenza vaccines. In addition, available sera from adult subjects may be further analyzed by the Sponsor to assess breadth of immune response induced by the study vaccines.

3 Description of the Overall Trial Design and Plan

3.1 Trial Design

GRC90 is a Phase IV, multi-center, open-label study of a planned 240 subjects to describe the safety and immunogenicity of Fluzone Quadrivalent vaccine in children 6 months to < 9 years of age and adults 18 to < 65 years of age, Flublok Quadrivalent vaccine in adults 18 to < 65 years of age, and Fluzone High-Dose vaccine in adults \geq 65 years of age.

Using a pre-programmed interactive response technology (IRT) system, each subject will be assigned to a vaccine group based on the subject's age at the time of enrollment. An approximately equal number of subjects from each group will be enrolled at each site.

Using the IRT system, subjects 18 to < 65 years of age will be randomly assigned to either Group 3 or Group 4. Enrollment in Group 3 and Group 4 will be stratified by age into 2 subgroups at each site so that approximately 50% of subjects at each site will be 18 to < 50 years of age and approximately 50% of subjects at each site will be 50 to < 65 years of age, so that an equal proportion of subjects within each age subgroup will receive either Fluzone Quadrivalent or Flublok Quadrivalent vaccine. If necessary to achieve 50% overall enrollment of subjects 50 to < 65 years of age and assignment of Fluzone Quadrivalent and Flublok Quadrivalent vaccines in a 1:1 ratio within each age subgroup (i.e., 18 to < 50 years of age and 50 to < 65 years of age), individual sites will be permitted to deviate from these ratios.

- Group 1: Children 6 to < 36 months of age assigned to receive a 0.25-mL dose of Fluzone Quadrivalent vaccine (30 subjects planned)
- Group 2: Children 3 to < 9 years of age assigned to receive a 0.5-mL dose of Fluzone Quadrivalent vaccine (30 subjects planned)
- Group 3: Adults 18 to < 65 years of age assigned to receive a 0.5-mL dose of Fluzone Quadrivalent vaccine (60 subjects planned)
- Group 4: Adults 18 to < 65 years of age assigned to receive a 0.5-mL dose of Flublok Quadrivalent vaccine (60 subjects planned)
- Group 5: Adults \geq 65 years of age assigned to receive a 0.5-mL dose of Fluzone High-Dose vaccine (60 subjects planned)

3.2 Trial Plan

All subjects will receive either a 0.25-mL (subjects 6 to < 36 months of age [Group 1]) or a 0.5-mL (subjects 3 to < 9 years of age and \geq 18 years of age [Groups 2, 3, 4, and 5]) intramuscular injection of study vaccine based on their assigned group at Visit 1. For subjects 6 months to < 9 years of age for whom 2 doses of influenza vaccine are recommended per the Advisory Committee on Immunization Practices (ACIP) guidance, a second intramuscular injection of Fluzone Quadrivalent vaccine (same 0.25-mL or 0.5-mL volume as administered at Visit 1) will be administered at Visit 2 (28 [window, 28–35] days after Visit 1).

Subjects 6 months to < 9 years of age (Group 1 and Group 2): blood specimens (approximately 5 mL) will be obtained from all subjects prior to the first vaccination at Visit 1 (Day 0) and 28 (window, 28–35) days following the final vaccination (Visit 2, if no study vaccine is administered at Visit 2; or Visit 3, if a second dose of study vaccine is administered at Visit 2) and assayed for immunogenicity. Staff will observe subjects for 20 minutes following study vaccine administration and will record the occurrence of any immediate unsolicited systemic adverse events (AEs). Subjects' parents/guardians will record information about solicited injection site and systemic reactions from Day 0 through Day 7 post-vaccination, and will record information about unsolicited non-serious AEs and serious adverse event (SAEs) from Visit 1 through Visit 2 for subjects receiving 1 dose of study vaccine, and from Visit 1 through Visit 3 for subjects receiving 2 doses of study vaccine.

Subjects ≥ 18 years of age (Group 3, Group 4, and Group 5): blood specimens (approximately 20 mL) will be obtained from all subjects prior to vaccination at Visit 1 and 21 (window, 21–28) days post-vaccination (Visit 2). Staff will observe subjects for 20 minutes following study vaccine administration and will record the occurrence of any immediate unsolicited systemic AEs. Subjects will record information about solicited injection site and systemic reactions from Day 0 through Day 7 post-vaccination, and will record information about unsolicited non-serious AEs and SAEs from Visit 1 through Visit 2.

Table 3.1: Study procedures 1 (Subjects 6 Months to < 9 Years of Age)

Study Flow Chart for Subjects 6 Months to < 9 Years of Age: 2 or 3 Visits, 1 or 2 Vaccinations

Visit Number	All Subjects		Subjects Receiving 1 Dose of Influenza Vaccine ^d	Subjects Receiving 2 Doses of Influenza Vaccine ^d		
	Visit 1 Day 0	Telephone Contact Visit 1 + 8 days	Visit 2 Visit 1 + 28 days	Visit 2 Visit 1 + 28 days	Telephone Contact Visit 2 + 8 days	Visit 3 Visit 2 + 28 days
Study Timelines	Day 0	Visit 1 + 8 days	Visit 1 + 28 days	Visit 1 + 28 days	Visit 2 + 8 days	Visit 2 + 28 days
Time Windows	--	+ 8 to 10 days	+ 28 to 35 days	+ 28 to 35 days	+ 8 to 10 days	+ 28 to 35 days
Informed consent/assent ^a	X					
Inclusion and exclusion criteria	X					
Demographic data	X					
Medical history	X					
Influenza vaccination history	X					
History-directed physical examination	X			X		
Temperature ^b	X			X		
Review contraindications for vaccination				X		
Allocation of subject number	X					
Blood sample (BL) ^c	BL1		BL2			BL2
Vaccination ^d	X			X		
Immediate surveillance (20 minutes)	X			X		
Diary card (DC) provided	DC1			DC2		
Telephone contact ^e		X			X	
Diary card reviewed and collected			DC1	DC1		DC2
Interim history			X	X		X
Termination record ^f			X			X
Serious adverse events	To be reported throughout the study period					

^a Informed consent form will be signed and dated by parent(s) or guardian(s) for subjects 6 months to < 9 years of age and assent form will be signed and dated by subjects 7 to < 9 years of age.

^b The preferred route for this study is rectal for subjects 6 to < 36 months of age, and oral for subjects 3 to < 9 years of age. The axillary route may be used when a rectal or oral temperature cannot be obtained.

^c A blood sample, approximately 5 mL, will be collected from all subjects at Visit 1, prior to vaccination, and at either Visit 2 (for subjects receiving 1 influenza vaccine dose) or at Visit 3 (for subjects receiving 2 influenza vaccine doses).

^d One or 2 doses of influenza vaccine will be administered according to the Advisory Committee on Immunization Practices guidance in effect during the study. If 2 doses of influenza vaccine are indicated, 1 dose will be administered during Visit 1 and the second dose (same 0.25-mL or 0.5-mL volume of Fluzone Quadrivalent vaccine as administered at Visit 1) will be administered approximately 28 days later during Visit 2.

^e The subject's parent/guardian will be contacted by telephone on Day 8 (window, Days 8–10) after vaccination as a reminder to complete the diary card and to bring it with them to the next visit.

^f The termination form will be completed at Visit 2 for subjects receiving 1 dose of influenza vaccine or at Visit 3 for subjects receiving 2 doses of influenza vaccine.

Table 3.2: Study procedures 2 (Subjects ≥ 18 Years of Age)

Study Flow Chart for Subjects ≥ 18 Years of Age: 2 Visits, 1 Vaccination

Visit Number	Visit 1	Telephone Contact	Visit 2
Study Timelines	Day 0	Visit 1 + 8 days	Visit 1 + 21 days
Time Windows		+ 8 to 10 days	+ 21 to 28 days
Informed consent	X		
Inclusion and exclusion criteria	X		
Demographic data	X		
Medical history	X		
Influenza vaccination history (previous season)	X		
History-directed physical examination	X		
Temperature ^a	X		
Urine or serum pregnancy test ^b	X		
Allocation of subject number	X		
Blood sample (BL) ^c	BL1		BL2
Vaccination	X		
Immediate surveillance (20 minutes)	X		
Diary card provided	X		
Telephone contact ^d		X	
Diary card reviewed and collected			X
Termination record			X
Serious adverse events	To be reported throughout the study period		

^a The preferred route for this study for subjects ≥ 18 years of age is oral.

^b Only for women of child-bearing potential.

^c A blood sample, approximately 20 mL, will be collected at Visit 1 and Visit 2.

^d Subjects will be contacted via telephone on Day 8 (window, Days 8–10) as a reminder to complete the diary card and to bring it with them to Visit 2.

4 Endpoints and Assessment Methods

4.1 Primary Endpoints and Assessment Methods

See Section 9.1 of the protocol.

4.2 Secondary Endpoints and Assessment Methods

See Section 9.2 of the protocol.

4.3 Observational Endpoints and Assessment Methods

See Section 9.3 of the protocol.

4.4 Derived Endpoints: Calculation Methods

4.4.1 Safety

4.4.1.1 Solicited Reactions

4.4.1.1.1 Daily Intensity

All daily records for solicited reactions will be derived into daily intensity according to the following classification: None, Grade 1, Grade 2, Grade 3, or Missing.

For measurable injection site reactions (erythema/swelling):

- For subjects 6 months to < 9 years of age
 - Grade 1: > 0 to < 25 mm
 - Grade 2: ≥ 25 to < 50 mm
 - Grade 3: ≥ 50 mm
- For subjects 18 years of age and older
 - Grade 1: ≥ 25 to ≤ 50 mm
 - Grade 2: ≥ 51 to ≤ 100 mm
 - Grade 3: > 100 mm

For measurable systemic reactions (i.e., fever):

- For subjects 6 months to < 36 months of age
 - Grade 1: $\geq 38.0^{\circ}\text{C}$ to $\leq 38.5^{\circ}\text{C}$, or $\geq 100.4^{\circ}\text{F}$ to $\leq 101.3^{\circ}\text{F}$
 - Grade 2: > 38.5°C to $\leq 39.5^{\circ}\text{C}$, or > 101.3°F to $\leq 103.1^{\circ}\text{F}$
 - Grade 3: > 39.5°C , or > 103.1°F

- For subjects 3 to < 9 years of age and 18 years of age and older
Grade 1: $\geq 38.0^{\circ}\text{C}$ to $\leq 38.4^{\circ}\text{C}$, or $\geq 100.4^{\circ}\text{F}$ to $\leq 101.1^{\circ}\text{F}$
Grade 2: $\geq 38.5^{\circ}\text{C}$ to $\leq 38.9^{\circ}\text{C}$, or $\geq 101.2^{\circ}\text{F}$ to $\leq 102.0^{\circ}\text{F}$
Grade 3: $\geq 39.0^{\circ}\text{C}$, or $\geq 102.1^{\circ}\text{F}$

For the derivation of daily intensities, the following sequential steps will be applied:

- 1) Solicited reactions (except fever/pyrexia) with an investigator presence recorded as “No” and with all daily records missing then all daily intensities will be derived as None.
- 2) For a temperature partially missing after decimal point, the data will be analyzed replacing “MD” (missing data) by zero. For example, a “39.MD” daily temperature will be considered as “39.0°C” at the time of analysis.
- 3) For non-measurable solicited reactions, the daily intensities will correspond to the daily records reported in the clinical database. For measurable solicited reactions, the daily measurements reported in the clinical database will be converted based upon the intensity scales defined in the protocol; this assumes that a reaction that is too large to measure (non-measurable, “NM”) is Grade 3. Note the intensity could be considered “None” (not a reaction) in the analysis despite being considered a reaction by the investigator (e.g., swelling measurement > 0 mm but < 25 mm in adults).

Note: The maximum intensity on the ongoing period is derived from the record of the maximum intensity/measurement after the end of the solicited period following the rule described above.

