4.4.1.1.2 Maximum Overall Intensity

Maximum overall intensity will be derived from the daily intensities computed as described in Section 4.4.1.1.1 and is calculated as the maximum of the daily intensities over the period considered.

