4.4.1.1.3 Presence

Presence is derived from the maximum overall intensity on the period considered:

- None: No presence
- Grade 1, Grade 2, or Grade 3: Presence
- Missing: Missing presence

Subjects with at least 1 non-missing presence for a specific endpoint will be included in the analysis. Conversely, those without a non-missing presence will not be included in the analysis of the endpoint.

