5.1.3.1 Safety

All analyses will be descriptive; no hypotheses will be tested.

The safety analysis will report the occurrence of solicited reactions and the incidence of unsolicited AEs between Visit 1 and Visit 2 (or between Visit 1 and Visit 3 for those subjects receiving 2 doses).

The number of subjects with documented safety will be used as denominator for the frequencies.

- For solicited reactions, the denominator will be the total number of subjects who have non-missing data for the endpoint considered
- For unsolicited AEs, the denominator will be the total number of subjects who were vaccinated with the dose analyzed

The safety tables will be produced using a subject approach; i.e., number of subjects who experienced at least 1 safety event during a considered period.

The 2-sided 95% CIs for the percentages will be calculated using the exact binomial method (Clopper-Pearson method).

Solicited reactions

The solicited injection site reactions and the solicited systemic reactions will be presented separately (except in summary tables).

Solicited reactions will be presented according to their nature (Medical Dictionary for Regulatory Activities [MedDRA, the latest version at database lock] PT), intensity (Grade 1, 2, or 3), time to onset, and number of days of occurrence.

Unsolicited AEs

Unsolicited AEs included in the analysis will be summarized in the safety overview and analyzed according to their nature (MedDRA [the latest version at database lock] system organ class [SOC] and PT classification) and relationship to the vaccination.

Injection Site Reactions

For each treatment group, the number and percentage of subjects experiencing any injection site reaction after injection will be calculated.

The description of injection site reactions will be presented according to:

- Solicited injection site reactions
All solicited injection site reactions that occur each day within 7 days after injection will be analyzed.
- Unsolicited injection site reactions
All unsolicited injection site reactions between Visit 1 and Visit 2 (or between Visit 1 and Visit 3 for those subjects receiving 2 doses) will be described according to the type of events.

Systemic Events and Reactions

For each treatment group, the number and percentage of subjects experiencing any unsolicited immediate systemic event in the 20 minutes after injection will be calculated.

In addition, the description of systemic events will be structured according to:

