5.3 Handling of Missing Data and Outliers

5.3.1 Safety

No imputation of missing data will be conducted. All subjects with safety data and all safety data recorded in the CRFs will be included in the safety analyses. No search for outliers will be performed. In all subject listings, partial and missing data will be clearly indicated as missing.

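### For solicited reactions other than fever, a subject with no daily records stays in the analysis if the investigator answered No but drops out if the answer was Yes

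*SAP*

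**What the plan says.** SAP 4.4.1.1.1 derives a daily intensity for each solicited reaction in sequential steps. Step 1 is limited to "Solicited reactions (except fever/pyrexia") and applies to a reaction "with an investigator presence recorded as “No” and with all daily records missing then all daily intensities will be derived as None". Step 2 concerns temperatures with a missing decimal. Step 3 takes everything else from the daily data: "For non-measurable solicited reactions, the daily intensities will correspond to the daily records reported in the clinical database", and measurable reactions are graded from their daily measurements. No step mentions an investigator answer of Yes with no daily records.

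The later derivations use only those daily intensities. Maximum intensity "is calculated as the maximum of the daily intensities over the period considered" (SAP 4.4.1.1.2). Presence follows from the maximum, with the line "Missing: Missing presence" for a missing one, and "those without a non-missing presence will not be included in the analysis of the endpoint" (SAP 4.4.1.1.3). For solicited reactions, "the denominator will be the total number of subjects who have non-missing data for the endpoint considered" (SAP 5.1.3.1).

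The general missing-data section, SAP 5.3.1, rules out imputation and adds: "All subjects with safety data and all safety data recorded in the CRFs will be included in the safety analyses". SAP 5.3.1.4 sends missing solicited intensities back to 4.4.1.1.1. The protocol has no rule for this case.

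**The concern.** Two subjects can have the same gap, no daily records for a given reaction, and differ only in what the investigator recorded. The SAP uses the answer when it is No and does not use it when it is Yes. Whether a subject stays in the analysis then depends on the outcome being measured, and the subjects lost are those with a recorded reaction.

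Solicited injection site and systemic reactions are safety endpoints 2 and 3 in protocol 9.3.1.2, and describing safety is one of the study's stated objectives. Elsewhere the SAP leans towards keeping events. An unsolicited event needs only a verbatim term and a grade other than 0 (4.4.1.2.1), missing causality is treated as related (5.3.1.2), and events with a missing onset are retained (5.3.1.5). A recorded solicited reaction without daily grades is handled less cautiously than any of these.

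The situation can arise. Cards are collected at Visit 2, 21 to 28 days after vaccination in adults and 28 to 35 days in children. Protocol 5.1.4 foresees cards that are not returned, and protocol 11.1 and 13.2 allow information obtained by interview to enter the case report book.

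**Working it through.** The documents give no reaction rate, missing-data rate or sample-size calculation bearing on this point, so there is no planned figure to reproduce.

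**1. Tracing the two answers (non-fever reaction, all daily records missing)**

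| Step | Investigator No | Investigator Yes |
|---|---|---|
| 4.4.1.1.1 daily intensity | None (step 1) | Missing (step 3, nothing to convert) |
| 4.4.1.1.2 maximum | None | Missing |
| 4.4.1.1.3 presence | Not present | Missing |
| 5.1.3.1 denominator | Counted | Left out |

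The exclusion in the right-hand column is not written as a rule. It results from the absence of a step combined with 4.4.1.1.3.

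**2. Effect in counts**

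Let N be the subjects in a group with either daily data or an investigator answer, R the reactors among them, and y the reactors with Yes but no daily records.

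- Rate under the SAP: (R − y)/(N − y)
- Rate if Yes is counted: R/N
- Difference: R/N − (R − y)/(N − y) = y(N − R)/[N(N − y)], which is positive whenever y > 0 and 0 < R < N

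Group sizes of 30 and 60 come from SAP 5.5; R and y are assumed. Intervals are 95% Clopper-Pearson, the method in SAP 5.1.3.1.

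| N | R | y | SAP rate | Yes counted |
|---|---|---|---|---|
| 60 | 30 | 3 | 27/57 = 47.4% (34.0 to 61.0) | 30/60 = 50.0% (36.8 to 63.2) |
| 60 | 18 | 3 | 15/57 = 26.3% (15.5 to 39.7) | 18/60 = 30.0% (18.8 to 43.2) |
| 30 | 15 | 2 | 13/28 = 46.4% (27.5 to 66.1) | 15/30 = 50.0% (31.3 to 68.7) |

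**3. Effect in expectation**

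Let p be the true rate and m the share of reactors with no daily records (assumed). The expected SAP rate is p(1 − m)/(1 − pm), so the shift is −pm(1 − p)/(1 − pm). For example, with p = 50% and m = 10%: 0.45/0.95 = 47.4%. Non-reactors without daily records stay in whatever their share, so only the share among reactors matters.

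Shift in percentage points:

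| p | m = 2% | m = 5% | m = 10% | m = 20% |
|---|---|---|---|---|
| 10% | −0.2 | −0.5 | −0.9 | −1.8 |
| 30% | −0.4 | −1.1 | −2.2 | −4.5 |
| 50% | −0.5 | −1.3 | −2.6 | −5.6 |
| 70% | −0.4 | −1.1 | −2.3 | −4.9 |

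**4. Fever**

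Step 1 exempts fever. With no temperatures recorded, Yes and No both end as missing, so the asymmetry is absent.

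**5. Adult erythema and swelling**

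In adults a size under 25 mm grades as None even if the investigator calls it a reaction, so a Yes without a measurement may or may not be a reaction in the analysis.

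- Suppose 30% of subjects have Yes, half of these are 25 mm or more whether or not measured, and m = 10% of Yes subjects lack records. The true rate is 0.30 × 0.5 = 15.0%, and the SAP gives 0.15 × 0.9/(1 − 0.03) = 13.9%.
- Suppose instead that 6 of 60 subjects have a graded reaction and 3 further Yes subjects, all below 25 mm, lack records. The SAP gives 6/57 = 10.5% against 6/60 = 10.0%.

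The sign depends on an unknown proportion.

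**The case against.** The strongest reply is that step 1 may reflect data entry: after a No, the daily fields may be left blank because there is nothing to grade. A No with blank fields would then be a complete negative answer, whereas a Yes with every day blank would be an obvious data gap that the site would be asked to fill. Several safeguards should keep such gaps few: the Day 8 call, follow-up of unreturned cards, interviews to clarify incomplete diaries (protocol 11.1), consistency checks and queries (11.2), verbal clarification (13.2), and resolution of all queries before database lock (13.4.1). This stands as an argument about frequency, and y may well be zero or close to it. It does not supply the missing rule: any Yes that remains without daily records is still dropped, and (R − y)/(N − y) applies without any assumption about the No subjects.

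The SAP also prefers measurements to the investigator's flag when deciding whether a reaction is ongoing (4.4.1.1.7). That does not settle this case, because no measurement exists and step 1 already relies on the investigator's answer.

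Three stronger inferences are tempting, and the documents do not support them.

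- A reader might infer that all solicited reaction rates are pushed down. Fever is exempt, and the direction for adult erythema and swelling is not determined.
- A reader might infer that 4.4.1.1.1 flatly contradicts 5.3.1. The general sentence there sits beside a no-imputation rule, and 5.3.1.4 refers back to the specific section. The two fit badly together, but a specific rule can qualify a general one.
- A reader might infer that dropping both kinds of subject would be a safe symmetrical cure. That is unbiased only if records are missing equally often in reactors and non-reactors. If blanks follow No by design, it would remove true non-reactors and raise the rates.

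**Conclusion.** The point holds for solicited reactions other than fever. Followed as written, the SAP loses recorded reactions while retaining recorded denials with the same missing data. Apart from adult erythema and swelling, the resulting rate is too low whenever such a case exists and 0 < R < N.

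The size rests on the assumed share m. At m = 10% the shift is at most about 2.6 points, small beside 95% intervals of roughly ±13 points (30/60) or ±19 points (15/30). The 20% column shows how the shift grows; nothing in the documents suggests that level. All analyses are descriptive, so no test or decision rule changes. It is worth correcting because the loss follows the outcome, concerns a safety endpoint, and would not be visible in the planned tables.

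**What to change.** Add a step to SAP 4.4.1.1.1, excluding fever and excluding adult erythema and swelling: if the investigator's presence answer is Yes and all daily records are missing, set presence to Yes and intensity to Missing. Count the subject in the numerator and denominator of the any-reaction rate, and show a missing-intensity row in the intensity tables. Since 4.4.1.1.3 derives presence from maximum intensity, it needs a matching cross-reference.

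The fever exclusion matters. Without it, a fever Yes would be counted while a fever No stayed missing, and the expected rate would become p/[1 − m(1 − p)], with m here the share without records in both reactors and non-reactors. At an assumed p = 10% and m = 10% that is 0.10/0.91 = 11.0%, and at m = 20% it is 0.10/0.82 = 12.2%: an upward bias that the present SAP does not have.

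For adult erythema and swelling, keep the main rule, do not exclude the No subjects, and add a sensitivity analysis that counts Yes subjects without measurements as present.

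Report the number of Yes subjects without daily records by group and reaction. If it is zero throughout, the issue is closed.

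The cost is one SAP sentence with its cross-reference, one table row, a small count table and a limited sensitivity analysis. Reported rates may be slightly higher.
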